25. Consent Process	13
26. Documentation of Consent	16
27. Study Test Results/Incidental Findings	16
28. Sharing Study Progress or Results with Subjects	17
29. Inclusion of Vulnerable Populations	18
30. Community-Based Participatory Research	19
31. Research Involving American Indian/Native Populations	19
32. Transnational Research	19
33. Drugs or Devices	20
Checklist Section	21
34. Export Control	22

PROTOCOL TITLE: Double-blind, placebo-controlled, randomized study of the safety and tolerability of isoxsuprine HCL combined with high dose steroid treatment of multiple sclerosis (MS) relapse

1. Objectives

Primary Objective

The primary objective of this study is to:

- Assess the safety and tolerability of Isoxuprine (ISX) in combination with high dose corticosteroids in subjects experiencing acute relapses due to multiple sclerosis.

The safety analysis population will include all randomized subjects who receive at least one dose of study drug. Safety endpoints will be summarized by treatment group (ISX or placebo) from the time of the first dose and include all available safety data. No formal statistical testing will be done. All adverse event data will be listed and will be summarized by treatment group. Quantitative safety variables (vital signs) will be summarized at each visit by treatment group and changes from baseline will be summarized by treatment group at selected visits.

Secondary Objective

The secondary objective of this study is to:

- Evaluate the potential efficacy of Isoxuprine as add-on treatment for improving neurological deficits in walking ability, visual acuity, and other associated symptoms of MS, including fatigue and cognitive dysfunction in this MS population experiencing a relapse.

The efficacy analyses will include all randomized and dosed subjects who provide Week 12 efficacy data. The key secondary analysis will compare the changes in EDSS functional system scores most relevant to the relapse associated disability (e.g. pyramidal, visual, cerebellar). Also walking speed and z-score from the Multiple Sclerosis Functional composite score (MSFC) from Baseline to Week 12 in the ISX group compared to the placebo group.

2. Background

Overview

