Those currently on MS disease modifying therapy will have received a stable regimen of the medications for at least 30 days prior to screening and will continue the same doses and regimens for the duration of their study participation.

Consented subjects will be assessed for relapse criteria and those who meet study eligibility criteria and agree to be treated with a standard 3 to 5 day pulse of high dose corticosteroids, will be randomized with equal probability to 1 of 2 treatment groups: placebo capsule or active Isoxsuprine (ISX).

The Screening Visit will take place within 7 days of relapse onset and within 48 hours of initiating high dose steroids. Subjects may start corticosteroids anytime during this 7 day window. During the screening period, subjects will be assessed with the Expanded Disability Status Scale (EDSS), Multiple Sclerosis Functional Composite (MSFC), and cognitive testing prior to treatment with ISX or placebo (1:1 ratio).

Safety Assessments during screening will include a physical exam, electrocardiogram, vital signs, weight and a urine pregnancy test for females of child bearing potential. At 7 (\pm 1) days following the completion of the 5-day ISX dosing, subjects will be re-assessed with the EDSS.

Subjects will be evaluated for treatment response using the EDSS and other standard measures described below at visits 1, 4 and 12 weeks.

Study drug will be administered as one (1) 10 mg capsule, 3 times daily for 5 days in conjunction with concomitant dosing with high dose corticosteroids. This can be any accepted regimen, including daily iv methylprednisolone 1000 mg/day or 600mg oral

PROTOCOL TITLE: Double-blind, placebo-controlled, randomized study of the safety and tolerability of isoxsuprine HCL combined with high dose steroid treatment of multiple sclerosis (MS) relapse

prednisone two times a day at approximately 8AM and noon, with food, as typically provided by UNM MS Specialty Clinic

4. Inclusion and Exclusion Criteria

Inclusion Criteria

Subjects must meet all the following criteria for inclusion in the study at the Screening Visit:

1. Subjects must be adequately informed and understand the nature and risks of the study and must be able to provide a signature and date on the ICF;
2. Male or female subjects between 18 and 50 years of age, inclusive;
3. Confirmed diagnosis of Multiple Sclerosis or Clinically Isolated Syndrome (CIS) suggestive of MS, according to the 2010 Revised McDonald criteria.

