4. On a stable regimen of medications taken specifically to treat MS for at least 30 days prior to screening, and willing to continue the same doses and regimens for the duration of study participation;
5. New neurological disability consistent with MS relapse no longer than 7 days prior to screening;
6. Screen visit and randomization must occur within 48 hours of subject initiating steroid treatment.
7. Maximum EDSS score during screening of 6.5;
8. Sufficient ambulatory ability (ambulatory aids acceptable if used consistently) to complete two trials of the Timed 25 Foot Walk (T25FW) at the screening visit with the two trials completed within 5 minutes of each other in accordance with the specific instructions provided by the National MS Society Functional Composite Manual.
9. Subject must be willing to take a high dose steroid (600mg oral prednisone two times a day (bid).
10. Subjects must have a mean systolic blood pressure \leq 160 and greater than 100 mm Hg and a mean diastolic blood pressure of \leq 100 and greater than 50 mm Hg determined by the average of 3 seated readings taken at least 5 minutes apart at the Screening Visit.
11. Subjects must be able to communicate effectively with study personnel. For this reason only English speaking subjects will be eligible for the study.
12. Subjects must be able and willing to follow all protocol requirements and study restrictions.
13. Subjects must be able and willing to return for all study visits.

PROTOCOL TITLE: Double-blind, placebo-controlled, randomized study of the safety and tolerability of isoxsuprine HCL combined with high dose steroid treatment of multiple sclerosis (MS) relapse

Exclusion Criteria

Subjects are ineligible for study participation if they meet any of the following criteria at the Screening Visit:

1. Subject is from a vulnerable population, as defined by the US CFR Title 45, Part 46, Section 46.111(b) and other local and national regulations, including but not limited to, employees (temporary, part-time, full time, etc) or a family member of the research staff conducting the study, or of the sponsor, or of the IRB.
2. Subject has only sensory, bowel/bladder, and/or cognitive symptoms of MS associated with the most recent relapse.
3. Subject has cognitive or behavioral impairment that in the opinion of the investigator would impair the ability of the subject to comply with study procedures.

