15. Inability to swallow oral capsules, or a history of gastrointestinal malabsorption that would preclude the use of oral medication;
16. If female, is pregnant or lactating;
17. History of hypersensitivity or allergic reaction to any of the study drugs.
18. History of heavy use of tobacco/smoking

5. Number of Subjects

Approximate Number of Subjects

Target enrollment is 20 subjects equally randomized to ISX or matching placebo.

6. Study Timelines

Approximate Duration of Subject Participation

Subjects will participate in the study for a total of up to 12 weeks. Study visits include a screening/randomization visit with drug administered and safety and efficacy assessment visits at weeks 1 (7 days after completion of ISX dosing), 4 and 12 weeks.

7. Study Endpoints

Primary safety endpoints will be assessed using the following:

- Individual GI symptoms
- Adverse events (AEs)
- Vital signs (temperature, respiratory rate, pulse, systolic and diastolic blood pressure)
- Electrocardiogram (ECG) parameters (heart rate, RR, QT, QTcF, QTcB, PR, and QRS intervals)

Secondary efficacy endpoints will be assessed using the following:

- Kurtzke Expanded Disability Status Scale (EDSS0)
- Timed 25-foot Walk (25FTW)
- Symbol Digit Modality Test (SDMT)

8. Research Setting

PROTOCOL TITLE: Double-blind, placebo-controlled, randomized study of the safety and tolerability of isoxsuprine HCL combined with high dose steroid treatment of multiple sclerosis (MS) relapse

Aside from recruitment which will take place at the Clinical Neuroscience Center, MS Clinic, all research activities will be completed at the MS Specialty Clinic. The MS Specialty Clinic is located at [name].

9. Prior Approvals

The following approvals are available and will be provided with study documentation:

- Departmental Review Form
- Drug Attachment for Isoxsuprine and matching placebo
- IND Exemption Checklist

10. Study Procedures

Screening Visit (Visit 1) Procedures/Assessments

The following procedures will be performed at the Screening Visit:

- Informed consent.
- Inclusion/exclusion criteria.
- Medical and surgical history.
- Demographics.
- Physical examination.
- EDSS.
- Multiple Sclerosis Functional Composite (MSFC).
- Cognitive Battery consisting of the Symbol Digit Modality test
- Height and Weight.
- Vital signs.
- Urine pregnancy test.
- Electrocardiogram (ECG) pre-dose.

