- Treat with oral prednisone (600 mg BID) if not already receiving corticosteroid pulse, which can be via Iv or Po route.
- Adverse events and concomitant medications.

Randomization Visit (Visit 1) Procedures/Assessments

- Initiate treatment with Isoxsuprine HCL (oral) Capsule 10mg or placebo.
- 1 hour monitoring post dose.
- Vital signs.
- Electrocardiogram (ECG) post dose.
- Adverse events.

1 Week Post Treatment Safety Follow-Up Visit (Visit 2) Procedures/Assessments

The following procedures will be performed at this visit:

- Physical examination.
- EDSS.

PROTOCOL TITLE: Double-blind, placebo-controlled, randomized study of the safety and tolerability of isoxsuprine HCL combined with high dose steroid treatment of multiple sclerosis (MS) relapse

- Multiple Sclerosis Functional Composite (MSFC).
- Vital signs.
- Adverse events and concomitant medications.

4 Week Post Treatment Safety Follow-Up Visit (Visit 3) Procedures/Assessments

The following procedures will be performed at this visit:

- Physical examination.
- EDSS.
- Multiple Sclerosis Functional Composite (MSFC).
- Cognitive Battery (Symbol Digit Modality).
- Vital signs.
- Adverse events and concomitant medications.

12 Week Post Treatment Safety Follow-Up Visit (Visit 4) Procedures/Assessments

The following procedures will be performed at this visit:

- Physical examination.
- EDSS.
- Multiple Sclerosis Functional Composite (MSFC).
- Cognitive Battery (Symbol Digit Modality).
- Vital signs.
- Adverse events and concomitant medications.

Adverse Events

Adverse events will be recorded from signing of the ICF and followed by the investigator until the AE is resolved or stabilized. Any and all safety measures (which includes standard of care activities) should be provided by the study site to the subject. Any study site follow-up should be documented.

Medical History

Medical history will be obtained at the Screening Visit. Medical history will include a review of the following systems: general medical and surgical history. Historical and current medical conditions including date of last menstrual period for female subjects will be recorded.

Current Medical Conditions

At each visit after screening, subjects will be asked about any changes in medical conditions, specifically new medical conditions and worsening of existing medical conditions. Any changes since the Screening Visit will be recorded as AEs, as appropriate.

Physical Examination

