After the PI has explained the trial and determined the subject's interest level, the designated research staff or "person obtaining consent" will verify the subjects understanding of the study, ensuring the subject has adequate information in making the decision to participate in the clinical trial. After all questions are answered, both subject and PI or authorized representative sign ICF.

A copy of the fully executed and signed ICF is provided to the subject for their records. The original ICF will be kept in the subject's study biner.

The full ICF process is completed prior to any study assessments and is documented in site's requisition form.

23. Study Test Results/Incidental Findings

Some diagnostic testing information will be given to the patient to include: Vitals, weight, Physical Exam. The patient will be given the information directly for them to share with their PCP.

24. Sharing Study Progress or Results with Subjects

Due to the length and the blinded nature of the study, there are no plans to share study progress or results with the study subjects at this time.

[figure not shown]
25. Inclusion of Vulnerable Populations

N/A This study does not seek to recruit participants from vulnerable populations.

26. Drugs or Devices

Product Description

Isoxsuprime hydrochloride (ISX)

Isoxsuprine hydrochloride structure

PROTOCOL TITLE: Double-blind, placebo-controlled, randomized study of the safety and tolerability of isoxsuprine HCL combined with high dose steroid treatment of multiple sclerosis (MS) relapse

Formulation and dosing: Compounded capsules with identical placebo, 10 mg by mouth 3 times per day for 5 days

Methods of Assigning Subjects to Treatment Groups

Subjects will be randomized 1:1 according to a computer-generated allocation scheme to receive either Isoxsuprine HCL 1 capsule 3 times daily for 5 days or matching placebo.

Emergency Identification of Investigational Medicinal Product

In case of an emergency during the study, when knowledge of the investigational product assignment is required for the medical management of an individual subject experiencing the emergency, the treatment blind for that subject may be broken by contacting the research pharmacy. The investigator must also indicate in source documents that the blind was broken and provide the date, time, and reason for breaking the blind.

Dosing Procedures

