This study proposes to use isoxsuprine HCl (ISX) in standard 10 mg tablets in subjects experiencing an acute relapse of multiple sclerosis. The rationale comes from strong preclinical observations that ISX had significant and novel neuroprotective action in ischemic stroke using a cell-based high-throughput screening (PLOS ONE, 1 May 2014, Volume 9 (5) e9676.). Isoxsuprine was identified as a top neuroprotectant among 1,200 compounds in the Prestwick Chemical Library, which contains diverse, mostly FDA-approved and off-patent compounds, and its neuroprotective function was confirmed in transient ischemic injury in animals. ISX has been used in the past for suppressing premature labor and for vascular dementia, since the drug is a beta-adrenergic agonist and vasodilator. These older indications are not used very often now but a typical dose was 10mg by mouth 3 to 4 times per day. In this tolerability and safety study we will use 10mg tid as the dose, given for 5 consecutive days. The primary goal is to assess safety and tolerability in MS patients in a relapse, who are also receiving a short course of high dose steroids to shorten relapse recovery. These subjects are otherwise healthy and will not have significant other health issues. We do not anticipate adverse reactions to concomitant use of ISX and steroids. While ISX tends to lower blood pressure modestly, steroids tend to increase, essentially in offsetting directions. Subjects will be randomized to ISX 10mg tid x 5 days or matching placebo. They will initiate the ISX within 48 hours of starting steroids.

PROTOCOL TITLE: Double-blind, placebo-controlled, randomized study of the safety and tolerability of isoxsuprine HCL combined with high dose steroid treatment of multiple sclerosis (MS) relapse

Checklist Section

This section contains checklists to provide information on a variety of topics that require special determinations by the IRB. Please complete all checklists relevant to your research.

I. Waivers or Alterations of Consent, Assent, and HIPAA Authorization

Partial Waiver of HIPAA Authorization for Screening/Recruitment

Complete the following additional questions/attestations if the records you will review to identify potential subjects and/or determine eligibility include Protected Health Information (PHI).

1. Will you be recording any PHI when conducting the records review to identify potential subjects and/or determine eligibility?

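### Baseline is steroid-free in some subjects and up to 48 hours into a steroid pulse in others: change from baseline within an arm cannot be read as an ISX effect, and with 10 per arm chance imbalance can distort the by-arm summaries

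*Protocol*

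**What the plan says.** Steroid timing is set in three places in the protocol.

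- Section 3 (Study Design): "Subjects may start corticosteroids anytime during this 7 day window", the window being the 7 days from relapse onset.
- Section 4, inclusion criterion 6: "Screen visit and randomization must occur within 48 hours of subject initiating steroid treatment".
- Section 10, Screening Visit list: "Treat with oral prednisone (600 mg BID) if not already receiving corticosteroid pulse, which can be via Iv or Po route". This item comes after EDSS, MSFC, the Symbol Digit test, vital signs and the pre-dose ECG.

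Baseline testing is tied only to the study drug: Section 3 requires EDSS, MSFC and cognitive testing before ISX or placebo, not before steroids.

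On allocation, Section 26 says "Subjects will be randomized 1:1 according to a computer-generated allocation scheme" and Section 3 speaks of equal probability. Neither names a stratification factor. Section 5 says "Target enrollment is 20 subjects equally randomized to ISX or matching placebo".

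On analysis, Section 1 says of vital signs that "changes from baseline will be summarized by treatment group at selected visits", without formal testing. The key secondary analysis there compares change from Baseline to Week 12 in functional system scores, walking speed and the MSFC z-score between arms.

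The protocol itself expects steroids to act on these measures. The IND waiver text in Section 26 says "While ISX tends to lower blood pressure modestly, steroids tend to increase, essentially in offsetting directions", and Section 2 says severe relapses may recover faster on high-dose steroids.

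**The concern.** Baseline does not mean the same thing in every subject. In one already on a pulse, baseline blood pressure may be raised by the steroid and some recovery may have begun. In one who starts steroids at Visit 1 after the baseline tests, neither applies. Later changes then include a steroid part that depends on which kind of subject it is.

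Vital signs are a primary safety endpoint and will be read from descriptive tables with about 10 subjects per arm. The ISX effect on blood pressure is expected to be modest and opposite in sign to that of steroids. A reader who takes the mean change in the ISX arm as the effect of ISX would be misled. A reader who compares the arms is protected on average, but not from an uneven split of pre-treated subjects in this one small trial.

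**Working it through.** The protocol states no power, effect size, SD or share of pre-treated subjects, so it has no figure to reproduce. The check asks how uneven the split can be, and what that does to the arm difference.

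**Inputs.** From the protocol: 20 subjects, 10 per arm, no factor named. Assumed: K = 6 to 10 of 20 already on steroids at baseline; steroids raise baseline systolic pressure by s = 5 to 10 mm Hg. The protocol gives only the direction.

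**Step 1: expected imbalance.** With random allocation, the number X of pre-treated subjects in the ISX arm is hypergeometric with mean K/2. The expected difference between arms, 2X − K, is 0 for every K.

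**Step 2: chance imbalance.** P(X = x) = C(K, x) × C(20 − K, 10 − x) / C(20, 10), with C(20, 10) = 184,756. The SD of the difference in pre-treated share is (2/10) × √[10 × (K/20) × (1 − K/20) × 10/19].

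| K | Allocations with a gap of 4 or more | Probability | SD of difference in share |
|---|---|---|---|
| 6 | 26,026 | 0.141 | 0.210 |
| 7 | 10,582 | 0.057 | 0.219 |
| 8 | 31,372 | 0.170 | 0.225 |
| 9 | 12,892 | 0.070 | 0.228 |
| 10 | 33,052 | 0.179 | 0.229 |

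The gap has the same parity as K, so for K = 7 or 9 a gap of at least 4 means at least 5. The range over K = 6 to 10 is about 6% to 18%. At K = 5 or 15 it is about 3%.

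**Step 3: effect on the arm difference.** Spurious difference = gap in share × s.

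- 7 v 3 (gap 0.4): 0.4 × 5 = 2 mm Hg to 0.4 × 10 = 4 mm Hg.
- A typical gap of one SD: 0.210 × 5 = 1.1 mm Hg to 0.229 × 10 = 2.3 mm Hg.
- For a disability score, if steroids have already shifted baseline by 0.5 to 1.0 point (assumed), a gap of 0.4 gives 0.2 to 0.4 point.

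**Step 4: added variance.** With half pre-treated and a steroid shift of r SDs, the SE of the arm difference is multiplied by √(1 + r²/4): 1.008 at r = 0.25 and 1.118 at r = 1.0. It rises by 0.8% to 12%.

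**Step 5: which visits.** Visit 2 falls 7 (±1) days after the 5-day ISX course ends. A 3 to 5 day pulse begun by Visit 1 is over by then.

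- *Visits 2 to 4:* the artefact comes from on-steroid baselines. Such a subject shows a fall once the pulse has ended; a subject with a steroid-free baseline does not. More pre-treated subjects in the ISX arm make its mean change look lower; fewer make it look higher.
- *Visit 1 post-dose:* steroid onset can enter in a subject with a steroid-free baseline, but only if the steroid is taken before the reading. Subjects are monitored for 1 hour after the study dose. The protocol gives no basis for a rise of 5 to 10 mm Hg that soon, so Step 3 should not be applied to this reading.

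**The case against.** A reader might infer that the mixed baseline biases the ISX v placebo comparison. It does not: both arms enter under the same steroid rule and allocation is random, so the steroid component cancels in expectation (Step 1). What remains is chance imbalance, which affects every unstratified factor in a trial of 20. That stands and limits the point.

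A reader might also infer that steroid onset could cancel or double a blood pressure fall caused by ISX. The visit schedule does not support this. After Visit 1, vital signs are next scheduled about a week after ISX has ended, so no on-treatment ISX fall is measured there to be masked.

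The size is also modest against noise. If the SD of systolic change is 8 to 14 mm Hg (assumed), the SE of the arm difference is SD × √(2/10) = 3.6 to 6.3 mm Hg. The 2 to 4 mm Hg shift is about one SE or less, in a descriptive summary. Section 15 says this is not an efficacy study.

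Finally, naming no stratification factor does not exclude one, and a covariate or table split may be in a statistical analysis plan not shown. Steroid timing must already be established to apply inclusion criterion 6, and concomitant medications are recorded, so a missing data field is not proven. These points stand. Against them, stratification has to be settled before the list is generated, and neither description of allocation in the protocol names a factor.

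**Conclusion.** The point holds in a limited form. Baseline is taken in mixed steroid states, so within-arm change in vital signs and disability cannot be attributed to ISX. The between-arm contrast is unbiased in expectation but open to chance imbalance: a gap of four or more pre-treated subjects has probability about 6% to 18%, and a 7 v 3 split gives about 2 to 4 mm Hg of spurious difference.

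These figures rest on two assumptions that the protocol does not supply: 6 to 10 of 20 subjects pre-treated, and a steroid effect of 5 to 10 mm Hg on baseline systolic pressure. The disability figures rest on a further assumed shift. The documents do not support a claim of systematic bias or of a masked on-treatment effect at follow-up. This is a cheap improvement to a small descriptive trial, not a flaw that invalidates it.

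**What to change.** - Stratify the 1:1 list by one two-level factor known at Visit 1: steroid pulse already started v first steroid dose at Visit 1. If the list already exists, use the factor as a covariate instead.
- Record the date and time of the first steroid dose.
- Show vital-sign change from baseline by arm together with steroid status at baseline.
- Include the factor in the EDSS, walking and MSFC comparisons.
- State that only the placebo-controlled difference will be interpreted, not the change within the ISX arm.

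With permuted blocks of 2 in each stratum, pre-treated counts differ by at most 1 between arms, so a 7 v 3 split cannot occur.

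The cost is a two-stratum list, one date and time field (if not already collected), one table split and one model term. Incomplete blocks may leave the arms off 10:10 by one or two subjects. The arm-by-status cells are small, about 3 to 7 subjects at the assumed shares if evenly split, so that table is for description only. The two-level factor treats 1 hour and 47 hours on steroids alike, which is why the time should be recorded. No steroid rule is changed.

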Multiple sclerosis (MS) is a disease of the central nervous system (CNS) characterized by multifocal inflammation, demyelination, axonal injury and brain atrophy secondary to neurodegenerative changes. The prevalence of MS in the US is estimated to be 1,000,000 in the US with approximately 2,000 new cases diagnosed annually. MS occurs more often in women than men (2:1 ratio) with a mean age of onset in the US of approximately 33 years. The most common pattern of MS is termed relapsing MS (RMS) where patients experience acute exacerbations or episodes of worsening neurological function followed by partial or complete recovery. Relapses of MS can be associated with transient or permanent disability. For this reason, it is common to treat significant relapse symptoms with short pulses of high dose corticosteroids. Severe relapses involving vision loss, impaired ambulation or other disabling symptoms may recover more quickly with high dose corticosteroids given daily for 3 to 5 days. Evidence from preclinical stroke models

PROTOCOL TITLE: Double-blind, placebo-controlled, randomized study of the safety and tolerability of isoxsuprine HCL combined with high dose steroid treatment of multiple sclerosis (MS) relapse

and experimental allergic encephalomyelitis suggest that isoxsuprine hydrochloride may have neuroprotective activity and reduce disability in animal models.

Ioxsuprine belongs to the group beta-agonists that cause vasodilation and has been used to treat problems resulting from poor blood circulation and, in certain women, to stop premature labor. Given its potential neuroprotective effects in CNS injury models, we propose to test it as a safe, tolerable add on treatment for acute relapses in patients with relapsing forms of MS.

3. Study Design

Description

This is a proof of concept, randomized, double-blind, placebo-controlled, 2-arm, parallel group study of Isoxsuprine in MS subjects experiencing a typical relapse.

All subjects will have a documented diagnosis of relapsing MS or a clinically isolated syndrome by international criteria. The relapse will be of sufficient severity that their physician recommends treatment with a high dose corticosteroid pulse. All subjects will have a physical examination and history with questions on drug sensitivities.

Subjects experiencing the onset of objective neurological deficits consistent with relapse within 7 days of randomization are eligible for screening for this study.

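### Does the unconditional wording of Inclusion 4 on a 30-day stable MS regimen conflict with Section 3 in a way that needs a change?

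*Protocol*

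**What the plan says.** Section 4 of the Protocol opens its inclusion list with a mandatory lead-in: "Subjects must meet all the following criteria for inclusion in the study at the Screening Visit". Item 4 then asks that the subject be "On a stable regimen of medications taken specifically to treat MS for at least 30 days prior to screening" and be willing to keep to it throughout participation. No condition limits the item to people who take such medication.

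Section 3 (Study Design) gives the same 30-day window and the same continuation requirement, but for a named group: "Those currently on MS disease modifying therapy will have received a stable regimen of the medications for at least 30 days prior to screening". It says nothing about people on no such therapy.

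On diagnosis, Section 3 states "All subjects will have a documented diagnosis of relapsing MS or a clinically isolated syndrome by international criteria", and Inclusion 3 asks for "Confirmed diagnosis of Multiple Sclerosis or Clinically Isolated Syndrome (CIS) suggestive of MS". Inclusion 5 sets the timing of the event: "New neurological disability consistent with MS relapse no longer than 7 days prior to screening".

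On the relapse steroids, Inclusion 6 reads "Screen visit and randomization must occur within 48 hours of subject initiating steroid treatment". The Screening Visit list in Section 10 provides for oral prednisone "if not already receiving corticosteroid pulse". Exclusion 7 bars recent systemic steroids only when they were given for something other than the MS relapse.

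**The concern.** Two current passages state the 30-day rule in different words, and they can be read to cover different people and different medicines.

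- **People.** Someone on no MS medication has no regimen to be stable on. Taken word for word, Inclusion 4 fails that person, while Section 3 does not touch them. The sharpest case is a first-event CIS patient. The event may be at most 7 days old at screening, so a patient with no earlier MS medication cannot show 30 days of it.
- **Medicines.** The phrase in Inclusion 4 looks wider than disease modifying therapy. A subject stable on disease modifying therapy who recently changed some other MS-specific medicine would satisfy Section 3 and might fail Inclusion 4. The phrase could even be stretched to the relapse steroid pulse.

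At stake would be who enters the trial and whether an untreated enrollee counts as an eligibility deviation. Under Section 16 the coordinator reviews records for excluding items before a screening visit is booked, so a literal reading could act early and leave little trace. With a target of 20, each subject is 1/20 = 5% of the sample.

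**Working it through.** No figure in the Protocol rests on this rule, so the check is a comparison of texts, followed by tracing the consequences.

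**1. The two statements side by side**

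| Element | Section 3 | Inclusion 4 |
|---|---|---|
| Window | at least 30 days before screening | at least 30 days before screening |
| Continuation | same doses and regimens throughout | same doses and regimens throughout |
| Who | those on disease modifying therapy | no condition stated |
| Which medicines | disease modifying therapy | medicines taken specifically for MS |

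The first two rows agree and the last two differ. The shared window and continuation requirement indicate one rule written twice.

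**2. Who is covered.** There are two ways to settle the difference.

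- If the condition in Section 3 is carried into Inclusion 4 (stable on whatever MS medication is taken, if any), the passages agree and untreated patients may enter.
- If Section 4 governs as written, untreated patients are out. Section 3 does not contradict this outright. It never declares them eligible, and it sends only those who meet the eligibility criteria on to randomization.

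The first reading leaves Inclusion 3 its full meaning. The second leaves the admission of CIS with little to act on at a first event, because the 7-day limit in Inclusion 5 and a 30-day treatment history can hardly both be met. That favors the first reading as the coherent one, but which population was intended is for the sponsor and investigator to say.

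**3. Which medicines are covered.** A conflict here needs a medicine that is specific to MS, is not disease modifying therapy and is not the relapse steroid. The Protocol names none as background treatment, and it does not define the phrase in Inclusion 4 as wider than disease modifying therapy. If the two terms are synonyms, nothing is left of this part.

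**4. The steroid pulse.** Inclusion 6 ties screening and randomization to the start of the pulse, Inclusion 9 requires willingness to take it, Section 10 allows for subjects already on it, and Exclusion 7 leaves steroids for the relapse outside its bar. Counting the pulse under Inclusion 4 would exclude subjects whom these items expect, so that reading fails on the document's own terms.

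**5. What the choice of reading changes in the trial**

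- *Bias:* eligibility is decided before the 1:1 computer-generated allocation in a double-blind trial, so either rule falls on both arms alike.
- *Consistency:* Section 8 places all research activities at one clinic, so there are no sites to diverge.
- *Analysis sets:* Section 1 defines the safety population by randomization and at least one dose, and the efficacy population by randomization, dosing and Week 12 data. Neither depends on Inclusion 4, so no subject would leave an analysis because of it.
- *Information:* Section 10 lists concomitant medications at screening and at all three follow-up visits, so background treatment can be described for every subject.
- *Recruitment:* the effect cannot be computed. The Protocol gives no share of patients who are untreated, at a first event, or recently changed in treatment.

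**The case for a change.** The strongest case for acting is that an eligibility list should mean what it says. The exclusion criteria state conditions where they are wanted: the pregnancy item is limited to women, and the depression item to patients with a history of major depressive disorder. Section 3 carries a condition for this very rule, and Inclusion 4 leaves it out under a lead-in that makes every item binding. Staff who follow Inclusion 4 literally could turn away patients at record review, while staff who follow Section 3 could enroll people who fail a mandatory item. The difference would also carry into follow-up, since both passages require the covered medicines to stay unchanged for up to 12 weeks. Eligibility belongs in the protocol rather than in an analysis plan, and aligning the two sentences would cost one clause and one shared term.

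What stands is that the wording differs, that Inclusion 4 lacks a condition, and that tidier text would be easy to write. What does not stand is the step from there to a consequence. Nothing in the Protocol shows that the coordinator would apply Inclusion 4 against Section 3. The follow-up version of the argument again needs an MS-specific medicine outside disease modifying therapy, and none is named. Whether an untreated enrollee is logged as a deviation is a matter of record-keeping that moves no subject out of either analysis population.

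**Conclusion.** This is a minor drafting inconsistency, and no change to the plan follows. Inclusion 4 omits the condition that Section 3 supplies. Read literally, it would bar untreated MS and first-event CIS patients whom Section 3 leaves alone. The choice of reading affects the make-up of the sample. It does not affect the validity of the randomized comparison or any stated number. Section 1 plans no formal testing of the safety endpoints, and Section 15 says the study is not powered to detect clinical benefit, so a somewhat wider or narrower background-treatment mix alters no planned conclusion.

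The judgment rests on three assumptions: that the single clinic applies one reading throughout, that concomitant medications are recorded as Section 10 lists them, and that the two medication terms were meant as the same thing. If the third fails, a few subjects with a recent change in another MS medicine could be classified differently. That too would be decided before allocation and would not bias the comparison. The size of any recruitment effect is unknown and cannot be derived from the Protocol.
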